#### 10.3 Data Analyses

#### 10.3.1 Survival outcome

Progression-free survival and overall survival will be estimated using the Kaplan-Meier approach and the corresponding confidence intervals will be estimated using Greenwood's formula. Distant metastases-free survival, local and regional control will be estimated using the Kaplan-Meier approach.

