#### 1.0 BACKGROUND AND RATIONALE

### 1.1 Disease Background

Until the recent developments of immunotherapy, we have reached a plateau in outcomes for locally advanced non-small cell lung cancer (LA-NSCLC). Despite aggressive therapy with concurrent chemoradiation, fewer than 20-25% of patients with stage III NSCLC achieve 5-year survival and are presumably cured. To date, modifications of chemotherapy or dose escalation of radiotherapy (RT) have not improved these outcomes.

Immunotherapy has significantly improved the survival outcomes of patients with various cancer types including thoracic malignancies. In the PACIFIC study, patients with locally advanced NSCLC were randomized to the anti-PDL1 antibody durvalumab or placebo for up to 12 months after completion of concurrent chemoradiation. Outcomes in the durvalumab arm were significantly better, regardless of tumor PDL1 status. Median PFS was 17.2 months in the durvalumab group (95% CI, 13.1 to 23.9) vs. 5.6 months (95% CI, 4.6 to 7.7) in the placebo group. The 24-month overall survival rate was 66.3% (95% confidence interval [CI], 61.7 to 70.4) in the durvalumab group vs. 55.6% (95% CI, 48.9 to 61.8) in the placebo group (two-sided P=0.005). (Antonia et al., 2018; Antonia et al., 2017). The time to death or distant metastasis was longer in the durvalumab group than in the placebo group (median, 28.3 months [95% CI, 24.0 to 34.9] vs. 16.2 months [95% CI, 12.5 to 21.1]; stratified hazard ratio, 0.53; 95% CI, 0.41 to 0.68). Following this study, consolidation durvalumab after chemoradiation received FDA approval and is now considered standard of care.

While NSCLC is typically considered relatively non-immunogenic, RT is thought to augment tumor immunogenicity(Iyengar & Gerber, 2013). The abscopal effect refers to the observation that RT to a local area results in an antitumor effect distant to the radiation site. One proposed mechanism for this phenomenon is inducing the release of circulating tumor antigen or inflammatory factors that could then mediate an augmented immune response against distant malignant lesions expressing similar tumor antigens. Supporting this hypothesis, local RT has been shown to increase the activity of natural killer cells (Uchida, Mizutani, Nagamuta, & Ikenaga, 1989).

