#### 10.0 STATISTICAL CONSIDERATIONS

#### 10.1 Study Design/Study Endpoints

- 10.1.1 Study design: The study is a single armed, phase II trial to evaluate concurrent Durvalumab and radiotherapy followed by consolidative Durvalumab for Stage III Non-Small Cell Lung Cancer (NSCLC).
- 10.1.2 Primary endpoint of 12-month progression-free survival (PFS) rate is based on an assessment by an investigators according to RECIST 1.1 criteria; PFS is defined as the time from the study enrollment to documented progressive disease or death due to any cause, whichever occurs first;
- 10.1.3 Secondary endpoint of safety and tolerability will be assessed by adverse event according to CTCAE V.5;
- 10.1.4 Secondary endpoint of overall survival is defined as the time from study enrollment to death due to any cause;
- 10.1.5 Secondary endpoint of distant metastases free survival is defined as the time from the study enrollment to any new distant lesion:

- 10.1.6 Secondary endpoint of local and regional control defined as the time from the study enrollment to any local and regional lesion:
- 10.1.7 Exploratory endpoint of biomarker and biomarker correlatives;
- 10.1.8 Exploratory endpoint of proportion of patients alive at 12 and 24 months.

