#### 10.2 Accrual

In the PACIFIC trial, patients who received consolidative durvalumab after chemoradiation had a 12-month PFS rate of 55%. PFS was measured starting after completion of chemoradiation, when anti-PDL1 treatment was started. This represents the assumed performance of the experimental arm in this study. We recognize that all patients who were randomized in the PACIFIC trial had tolerated and not progressed on chemoradiation, which represents some degree of selection bias. The possibility of early progression or treatment intolerance were taken into account when selecting the margins for the non-inferiority design of this study. A sample size of 47 achieves 80% power to detect a non-inferiority against an upper hazard ratio of 1.4 using a log-rank test at a 0.1 significance level when the actual hazard ratio is 1.0 and the standard of care group hazard rate is 0.5978 (which is equal to 1-year PFS rate of 55% using an exponential model). Three additional patients will be enrolled (total N=50) to account for 5% loss to follow-up. Patients will be accrued for a period of 3 years with 1-year follow-up.

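### Kaplan-Meier for local and regional control censors patients who die without local-regional failure, so it overstates failure; the size depends on rates the plan does not give

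*Combined protocol and SAP*

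**What the plan says.** The endpoint is given in the same terms in sections 2.2.4, 2.4.5 and 10.1.6; the last reads "Secondary endpoint of local and regional control defined as the time from the study enrollment to any local and regional lesion". Death is not part of the event.

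The analysis is in section 10.3.1: "Distant metastases-free survival, local and regional control will be estimated using the Kaplan-Meier approach". The Study Summary repeats it. Greenwood confidence intervals are specified for PFS and OS, but no interval is specified for local and regional control. The plan gives no censoring rule for this endpoint, no time point at which it will be reported, and no mention of competing risks or cumulative incidence.

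Two other sections bear on the point. Section 10.2 plans 3 years of accrual and 1 year of follow-up. Section 4.6 (Duration of Follow Up) says that patients are followed for survival once progression is documented; it does not say that local assessment continues.

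**The concern.** Leaving death out of the event is reasonable for a site-specific control endpoint. The difficulty is the estimator. Kaplan-Meier treats a censored patient as someone who would go on to fail at the same rate as those still under observation, and a patient who has died cannot. So 1-KM describes a hypothetical population in which nobody dies, and even that reading requires death and local failure to be independent. It is not the proportion of enrolled patients who fail locally.

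Deaths will not be rare. For the durvalumab arm of the PACIFIC trial, section 1.1 reports: "The 24-month overall survival rate was 66.3% (95% confidence interval [CI], 61.7 to 70.4) in the durvalumab group". About one patient in three had died by then. The present trial removes chemotherapy from curative-intent radiotherapy, and section 1.4 asks whether outcomes are comparable to chemoradiation followed by durvalumab. In a single-arm study the local failure rate can only be read against other series, and an estimate that rises with the trial's own death rate is hard to compare with series that had different mortality.

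**Working it through.** **1. The plan's own figures.** There is no stated figure for local-regional failure to reproduce. The nearest one is the PFS hazard in section 10.2: "standard of care group hazard rate is 0.5978 (which is equal to 1-year PFS rate of 55% using an exponential model". It reproduces: -ln(0.55) = 0.5978 per year. The sample size of 47 also reproduces, as a one-sample log-rank test with one-sided alpha 0.1, 80% power, a margin of 1.4, a true hazard ratio of 1.0, and uniform accrual over 3 years plus 1 year. The event probability is 0.744 and N = ((1.2816 + 0.8416 × √(1/1.4)) / (1 − 1/1.4))² / (1.4 × 0.744) = 46.7, rounded up to 47. Neither figure uses local control.

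**2. Direction.** Let f be the hazard of local-regional failure and d the hazard of death without it, both constant.

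- Kaplan-Meier with deaths censored estimates 1-KM(t) = 1 − exp(−f t).
- The probability of failure is CIF(t) = f/(f+d) × (1 − exp(−(f+d) t)).

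The first is the integral of f exp(−f s) from 0 to t. The second is the integral of f exp(−(f+d) s). The second is smaller whenever f and d are both above zero, so the sign of the bias needs no numerical input.

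**3. Inputs for the size (assumptions).**

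- d: a 24-month OS of 66.3% implies an all-cause hazard of −ln(0.663)/2 = 0.2055 per year. Some deaths follow local failure, so d is taken as 0.10 to 0.20, from about half of this to nearly all of it.
- f: 0.1 to 0.3 per year. The documents give no value. The upper end is about half the PFS hazard (0.5978/2 = 0.299).
- Horizon: 24 months, and 4 years (3 + 1) as the longest follow-up at the planned analysis.

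**4. Results** (gaps taken before rounding).

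| f | d | 24 months: 1-KM / CIF / gap | 4 years: 1-KM / CIF / gap |
|---|---|---|---|
| 0.1 | 0.10 | 18.1% / 16.5% / 1.6 | 33.0% / 27.5% / 5.4 |
| 0.2 | 0.15 | 33.0% / 28.8% / 4.2 | 55.1% / 43.1% / 12.0 |
| 0.3 | 0.20 | 45.1% / 37.9% / 7.2 | 69.9% / 51.9% / 18.0 |

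The middle row at 24 months: 1 − exp(−0.4) = 0.330, and (0.2/0.35) × (1 − exp(−0.7)) = 0.5714 × 0.5034 = 0.288.

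**5. Sensitivity at 24 months**, with f from 0.05 to 0.30.

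| Competing hazard | Gap (points) |
|---|---|
| d = 0.1027 (half of all-cause) | 0.9 to 3.9 |
| d = 0.2055 (all of it) | 1.7 to 7.4 |
| Death 3 times as likely after local failure, OS held at 66.3% | 1.6 to 5.3 |
| d = 0.2935, from the placebo arm's 55.6% 24-month OS | 2.3 to 10.0 |
| Any first non-local PFS event competes (d = 0.5978 − f) | 3.7 to 10.1 |

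The direction never changes, and the size runs from about 1 to about 10 points. Taking only a quarter of the all-cause hazard, an extreme choice, gives 0.5 to 2.0.

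**6. Distant progression first.** If local assessment stops at distant progression and the patient is censored there, a later death never enters as a competing event. Naming death alone would then move the cumulative incidence estimate back toward 1-KM. The last row of the table shows that this group can matter as much as death.

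**The case against.** Several points on the other side stand.

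- **The size is assumed.** A reader might take 2 to 7 points, or any single range, as an established error. The documents do not support that: they give neither a local-regional failure rate nor a rate of death without it. The one anchored input comes from another trial's patients who, as section 10.2 acknowledges, had already completed chemoradiation without progressing. The upper end also needs local failure to have little effect on mortality. When death is made three times as likely after local failure, the 24-month maximum falls to 5.3 points.
- **Five years is not the planned horizon.** The hazards in step 4 give 7.7 to 22.6 points at 5 years, and it is tempting to lead with that. No patient has more than 4 years of follow-up at the planned analysis. Visits and CT continue beyond that, but no 5-year local control estimate is planned.
- **Precision is limited.** With 50 patients and failure near 33%, the binomial standard error is √(0.33 × 0.67/50) = 6.6 points, so the central 24-month bias of 4.2 points is below one standard error. It is nonetheless systematic and avoidable.
- **No decision hangs on this estimate.** Local control has no threshold, test or named comparator. The secondary objectives call for comparison with historical data only for safety (2.2.1). The bias also runs against the regimen, so it cannot produce a falsely favourable claim of control.
- **Kaplan-Meier local control is customary.** That is a reason to keep such a curve as a supplementary display, but not as the only estimate of the failure rate.

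These points limit the size and consequence of the problem. None of them makes 1-KM the probability of local-regional failure.

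**Conclusion.** The concern holds as a matter of method. The event definition in 10.1.6 and the estimator in 10.3.1 together force deaths without local-regional failure to be censored, so failure is overstated and control understated. The sizes in the working rest on constant hazards and on assumed rates for both events, and should be cited only as illustrations.

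A reader might also infer that the trial's main conclusion or its sample size is compromised. It is not. PFS as defined in 2.4.1 and 10.1.2 counts death as an event, and the sample size is built on PFS. (Section 6.1.6 leaves death out of PFS and should be aligned, but that is a separate matter.) The wording of the lesion definition, and whether distant metastases-free survival should count death, are also separate. What is affected is a descriptive secondary endpoint.

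**What to change.** In section 10.3.1, replace Kaplan-Meier for this endpoint with wording along these lines: the cumulative incidence of local-regional failure as first event will be estimated by the Aalen-Johansen method with a 95% confidence interval; death without local-regional failure and distant progression occurring first will be competing events and will not be censored. Keep Kaplan-Meier for PFS and OS. A cause-specific Kaplan-Meier curve for local control may be kept as a labelled secondary display for comparison with older series.

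Treating distant progression first as a competing event matches the follow-up stated in section 4.6. It narrows the question to local-regional failure as first event, and the report should say so.

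The cost is a sentence or two and slightly more analysis work in standard software. No new data are needed, because the dates of death and of first progression are already required for OS and PFS; the site of first progression must be recorded. The downside is less direct comparability with series that report Kaplan-Meier local control, which the secondary display partly offsets.

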#### 10.3.2 Toxicities:

Only adverse events assessed to be definitely, probably, or possibly related to protocol treatment will be considered. Toxicity rate and it confidence interval will be estimated using an exact binomial approach.

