# UTSouthwestern Harold C.Simmons Comprehensive Cancer Center

[figure not shown]
of MEDI4736 in adult patients with advanced solid tumours, refractory to standard therapy (Study CD-ON-MEDI4736-1108). The safety profile of durvalumab in this population was consistent with that of other immunotherapies and with its known safety profile as monotherapy in patients with more advanced disease (stage IIIB or IV NSCLC)(Antonia SJ). Safety data are available for the 20 patients in the Q2W dose-escalation cohorts. Nineteen of the 20 patients treated at the Q2W schedule have reported at least 1 treatment-emergent AE. No patient has had a DLT at doses up to 10 mg/kg. The most frequent treatment-emergent AEs reported in 3 or more patients included fatigue (6 patients), constipation, decreased appetite, diarrhoea, dyspnoea and nausea (4 patients each), and cough, dehydration, hypertension, pyrexia and rash (3 patients each). Seven patients have had an AE that has been considered by the reporting investigator to be related to treatment: diarrhoea, vomiting, fatigue, dizziness and rash (2 patients each), and anaemia, nausea, influenzalike illness, infusion-related reaction, dehydration, and pruritus (1 patient each). The majority of AEs (in 15 of the 20 patients) have been Common Terminology Criteria for Adverse Event (CTCAE) Grade 1 or 2. There have been no Grade 3 or higher treatment-related AEs. One patient (in the 1.0 mg/kg cohort) had 2 events of Grade 3 hyponatremia, which occurred in the setting of dehydration. Four patients (1 patient in each of the 0.1, 0.3, 3.0, and 10.0 mg/kg cohorts) died due to AEs. None of the events were considered by the reporting investigator to be related to treatment. Three of these deaths were due to progression of disease (PD) recorded as serious adverse events (SAEs); the fourth death was due to retroperitoneal haemorrhage.

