In addition to trials in advanced disease, durvalumab was investigated in stage III non-resectable NSCLC in the PACIFIC trial. In this study, patients were randomized to durvalumab 1500 mg IV or placebo every 14 days for up to one year, following completion of concurrent chemoradiation. The durvalumab arm demonstrated improved PFS and OS compared to the placebo arm (Figure 1). Tumor PD-L1 expression was tested retrospectively using archival tumor tissue obtained prior to chemoradiotherapy. Durvalumab improved overall survival for all but PD-L1 <1% group (Figure 2A). Durvalumab also improved progression-free survival in each of the PD-L1 subgroups (Figure **2 B).** Limitations of PD-L1 subgroup analyses include the post-hoc nature with no pre-specified statistical adjustmetn, incomplete sample collection and small sample size of subgroups, the low number of events resulting in imbalances in baseline clinical characterisitics. The most common treatment-related adverse events included cough, pneumonitis, dyspnea, fatique and diarrhea. Apparent immune-related adverse events included pneumonitis, pruritis and rash. Table 1 lists AEs by treatment arm and severity. Pneumonitis, arguably the greatest concern in a trial combining sequential thoracic chemoradiation and immune checkpoint inhibition, was numerically increased in the durvalumab arm, but severe cases remained less than 5%: 33.9 (3.4% grade 3-4) in the durvalumab arm versus 24.8% (2.6% grade 3-4) in the placebo arm. Toxicity event terms that could represent similar processes, such as dyspnea and pneumonia, occurred at comparable rates between durvalumab and placebo arms, and reached grade 3-4 in fewer than 5% of patients. The use of combination therapies may contribute to the increased incidnece of penumonitis in the PACIFIC trial compared to the previously reported 3-5% (Suresh et al., 2018). Additionally, most cases of pneumonitis were reversible with stopping treatment, initiating glucocorticoids, or both.

Figure 1. Overall Survival (A) and Progression Free Survival (B) in PACIFIC study (A)

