#### 6.2 Safety/tolerability

Analyses will be performed for all subjects having received at least one dose of study therapy. The study will use the CTCAE version 5.0 for reporting of adverse events. https://ctep.cancer.gov/protocolDevelopment/electronic applications/ctc.htm

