# 7.3 Steps to Determine If a Serious Adverse Event Requires Expedited Reporting to the SCCC DSMC and/or HRPP

Step 1: Identify the type of adverse event using the NCI Common Terminology Criteria for Adverse Events (CTCAE v5).

Step 2: Grade the adverse event using the NCI CTCAE v5.

Step 3: Determine whether the adverse event is related to the protocol therapy. Attribution categories are as follows:

- Definite The AE is clearly related to the study treatment.
- Probable The AE is likely related to the study treatment.
- Possible The AE may be related to the study treatment.
- Unlikely The AE may NOT be related to the study treatment.
- Unrelated The AE *is clearly NOT related* to the study treatment.

Note: This includes all events that occur within 30 days of the last dose of protocol treatment. Any event that occurs more than 30 days after the last dose of treatment and is attributed (possibly, probably, or definitely) to the agent(s) must also be reported as indicated in the sections below.

Step 4: Determine the prior experience of the adverse event. Expected events are those that have been previously identified as resulting from administration of the treatment. An adverse event is considered unexpected, for expedited reporting purposes only, when either the type of event or the severity of the event is not listed in:

- the current known adverse events listed in the Agent Information Section of this protocol (if applicable);
- the drug package insert (if applicable);
- the current Investigator's Brochure (if applicable)
- the Study Agent(s)/Therapy(ies) Background and Associated Known Toxicities section of this protocol

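### Section 10.3.2 analyses only adverse events judged at least possibly related, although the safety endpoint and the adverse event definition carry no attribution condition; the all-cause rate should be reported beside the related-only rate.

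*Combined protocol and SAP*

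**What the plan says.** The toxicity analysis in Section 10.3.2 has two sentences. The first sets the filter: "Only adverse events assessed to be definitely, probably, or possibly related to protocol treatment will be considered". The second says that the toxicity rate and its confidence interval will be estimated by an exact binomial method. No other section specifies a toxicity rate with an interval.

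The sections that this analysis serves are wider:

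- **Endpoint (2.4.2, repeated in 10.1.3).** Safety and tolerability are assessed by adverse events under CTCAE version 5, with no mention of attribution.
- **Definition (7.2.1).** An adverse event counts as one regardless of whether it is thought to be related to the research.
- **Monitoring (7.2).** Events are followed whatever their relationship to therapy.
- **Objective (2.2.1).** The first secondary objective compares safety and tolerability with historical data from standard chemoradiation. Section 1.4 adds the hypothesis that the new regimen will be better tolerated.

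Section 6.2 gives the denominator: "Analyses will be performed for all subjects having received at least one dose of study therapy".

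**The concern.** Events judged unlikely or unrelated are followed during the trial and then left out of the only planned estimate of the safety endpoint. The study is open label and has no concurrent control, so nothing inside it shows how attribution affects the rate. A reader who sees a low related-only rate cannot tell whether patients had few events or whether many events were put down to other causes.

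The comparison in 2.2.1 adds a second difficulty. Two rates can be compared only if they count events in the same way. The documents name no historical source for this objective and so give no attribution rule for it. If only the related rate is available, it may have no valid counterpart.

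**Working it through.** The documents state no toxicity rate, threshold or interval for this trial, so there is no planned figure to reproduce. The check is a comparison of the text, followed by a sense of scale.

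**1. Direction of the filter.** An exact binomial interval implies a rate per patient. Let *a* be the number of patients with at least one qualifying event of any cause, *r* the number with at least one qualifying event judged definitely, probably or possibly related, and *n* the number treated. Every patient counted in *r* is also counted in *a*, so r/n ≤ a/n. The gap is (a − r)/n: the share of patients whose qualifying events were all judged unlikely or unrelated. It is zero if there are no such patients.

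**2. Scale at the planned size.** Section 10.2 plans 50 patients. One such patient moves the rate by 1/50 = 2.0 percentage points.

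**3. Range under assumed attribution.** Suppose 15 of 50 patients have a severe event of any cause. This is a round count, close to the 29.9% with any grade 3 or 4 event in the durvalumab arm of Table 1, Section 1.2, which does not state its attribution basis. The shares judged related are assumptions. The intervals are exact (Clopper-Pearson), with limits Beta(0.025; x, n − x + 1) and Beta(0.975; x + 1, n − x). The 95% level is also an assumption, since 10.3.2 gives none.

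| Share of the 15 judged related | Counted | Rate | 95% CI | Gap from all-cause |
|---|---|---|---|---|
| 100% (equals all-cause) | 15/50 | 30% | 17.9 to 44.6 | 0 points |
| 80% | 12/50 | 24% | 13.1 to 38.2 | 6 points |
| 60% | 9/50 | 18% | 8.6 to 31.4 | 12 points |
| 40% | 6/50 | 12% | 4.5 to 24.3 | 18 points |

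**4. An example from the protocol.** Section 1.2 reports both counts for one group given durvalumab, the 20 patients of the Study 1108 dose-escalation cohorts. On the all-cause side: "Nineteen of the 20 patients treated at the Q2W schedule have reported at least 1 treatment-emergent AE". On the related side: "Seven patients have had an AE that has been considered by the reporting investigator to be related to treatment".

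- All-cause: 19/20 = 95% (exact 95% CI 75.1 to 99.9).
- Related: 7/20 = 35% (15.4 to 59.2).
- Gap: 12/20 = 60 points.

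This shows that the two rates can differ widely in the same patients. It is not a forecast: those patients had refractory advanced solid tumours and received no radiotherapy as part of that regimen, and the doses began at 0.1 mg/kg.

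**The case against.** The strongest reply is that 10.3.2 makes an open analysis choice and does not contradict the rest of the plan. An analysis section may narrow a broadly worded endpoint, the definition in 7.2.1 governs collection and reporting, and the filter still admits events judged only possibly related. This stands in part. A related-only rate is a legitimate summary and should be kept. The reply does not justify having it as the only one.

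It can also be said that all-cause events remain visible. Section 10.3.4 tabulates adverse events twice a year with no filter, the data safety monitoring committee reviews adverse events quarterly (11.4), and all serious events are reported whatever their cause (7.3.2). No decision rule in Section 10 uses the 10.3.2 rate. All of this is correct, and it means that the plan does not conceal events from those who oversee safety. These are monitoring outputs, however, and not the endpoint estimate with its interval.

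Three stronger readings are tempting, and the documents do not support them:

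- *The filter favours the new regimen in the historical comparison.* That follows only if the historical rates are all-cause. If they are related-only, there is no automatic direction. No source is named.
- *The safety population in 6.2 conflicts with the filter.* Section 6.2 says which patients are analysed, not which events are counted.
- *Study 1108 also gives a firm gap for severe events.* Section 1.2 reports none of grade 3 or higher judged related, alongside one patient with grade 3 hyponatremia and four deaths due to adverse events. But three of those deaths were from progression, and the accompanying statement on grade 1 or 2 events in 15 of the 20 patients can be read in more than one way. No severe-event count is relied on here.

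**Conclusion.** The point holds as a cheap improvement. Followed as written, 10.3.2 yields a rate equal to or below the all-cause rate, and the difference rests on investigator judgement with no control group. Its size in this trial is unknown: 2.0 points per affected patient at n = 50, possibly zero, and 6 to 18 points only under the assumed starting count and attribution shares shown above. The related-only rate cannot be set against historical data whose attribution rule differs or is not known, and the direction of any bias in that comparison cannot be stated from the documents. The conclusion assumes that the toxicity rate is per patient, as the binomial method implies. The primary endpoint, sample size and conduct of the trial are unaffected.

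**What to change.** In 10.3.2, replace the restriction with wording along these lines:

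> Adverse event rates will be reported both for all causes and for events judged definitely, probably or possibly treatment-related. Each will be given for any grade and for grade 3 or higher, with an exact binomial confidence interval, in all patients who received at least one dose, over the acute period ending 90 days post treatment.

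For objective 2.2.1, set against each historical source the rate that uses the same attribution rule. Where a source does not state its rule, say so beside the comparison.

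The cost is a few lines of text and one additional set of rates. Section 7.2 already follows events regardless of relationship, and the acute period of 7.2.1 already runs to 90 days post treatment. One item needs confirming: the attribution steps in 7.3 are written for expedited reporting of serious events, and their note requires events more than 30 days after the last dose only when attributed to treatment. The case report form should therefore record every adverse event, with its attribution, for the full 90 days.

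The downside is a higher headline rate that includes some events due to progression or comorbidity. In Study 1108, for example: "Three of these deaths were due to progression of disease (PD) recorded as serious adverse events (SAEs". That is why the related-only rate should stay alongside.
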